#### **14.1.1. Analysis Set**

##### **14.1.1.1. Safety analysis set**

Safety analysis set includes all subjects who received any dose of IP. The safety, pharmacodynamics, and anti-drug antibody analyses will be based on the safety analysis set.

##### **14.1.1.2. Efficacy evaluable set**

Efficacy evaluable set includes all subjects who received the revised regimen of Thymoglobulin and steroids, and any dose of IP. The efficacy analysis will be based on the efficacy evaluable set.

#### **14.1.1.3. Pharmacokinetic analysis set**

Pharmacokinetic (PK) analysis set includes all subjects who received IP and have at least one quantifiable plasma PK observation post-first dose. The PK analysis will be based on the PK analysis set.

#### **14.1.2. Procedure for Accounting for Missing Data**

All analyses will be based on actual observed data. Missing values will not be imputed.

### **14.2. Statistical Methods**

#### **14.2.1. Efficacy**

##### **14.2.1.1. Primary Efficacy Endpoint**

The primary efficacy variable is the incidence of efficacy failure, defined as treated biopsy-proven acute rejection (tBPAR) of grade 1A or higher, graft loss or death, at Week 24 post-transplantation. For the primary analysis the acute rejection rating will be based on the consensus of the pathologists at the initial two participating sites.

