A graft core biopsy must be performed within 48 hours for all cases of suspected acute rejection (based on the investigator's clinical judgment), regardless of initiation of anti-rejection treatment. Biopsies will be read by local pathologist according to Banff criteria 2017 (Haas, Loupy et al. 2018) and will be used to guide patient management. In addition, all subjects will undergo surveillance renal biopsies following reperfusion of the allograft on Day 0 and again at the end of Week 24.

- Subjects with mild cellular rejection (Banff Grade 1A or 1B) will be treated with corticosteroids and continue treatment with VIB4920 + belatacept.
- Subjects with Banff Grade 2A lesions will be treated with corticosteroids, then re-biopsied (at investigator's discretion), and will continue treatment with VIB4920 +

belatacept if the repeat biopsy shows resolution of acute rejection or transitioned to standard of care immunosuppression for persistent or worsening lesions.

- Subjects with BPAR of Banff Grade  $\geq$  2B, or any antibody mediated rejection, must discontinue treatment with VIB4920, with subsequent management at the discretion of the investigator.

Following completion of all required evaluations at the Week 48 visit, subjects will be followed for an additional 12 weeks for safety while receiving standard of care management at the investigator's discretion.

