## 9.5. Randomization and Blinding

This is a single-arm, open-label study. No randomization or blinding will be used.

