3.5.1.2 Primary efficacy analysis

For the primary efficacy analysis, the acute rejection rating will be based on the consensus of the pathologists at the 2 participating sites.

The primary efficacy endpoint will be analyzed descriptively. The incidence of efficacy failure, defined as tBPAR of grade 1A or higher, graft loss, or death at Week 24 post-transplantation, and the corresponding 80% 2-sided exact confidence interval will be calculated. Missing data will not be imputed.

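### The consensus reading that sets the primary rejection grade is not masked to the local grade, treatment or clinical course, so a lenient call near grade 1A would enter an uncontrolled failure count directly

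*Protocol*

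**What the plan says.** The primary endpoint is efficacy failure at Week 24: treated biopsy-proven acute rejection (tBPAR) of grade 1A or higher, graft loss or death. On who grades the rejection, Protocol 14.2.1.1 states: "For the primary analysis the acute rejection rating will be based on the consensus of the pathologists at the initial two participating sites". SAP 3.5.1.2 says that "the acute rejection rating will be based on the consensus of the pathologists at the 2 participating sites".

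Protocol 7.1 sets up a second reading of the same tissue: "Biopsies will be read by local pathologist according to Banff criteria 2017", and those readings "will be used to guide patient management". Treatment follows the local grade: "Subjects with mild cellular rejection (Banff Grade 1A or 1B) will be treated with corticosteroids". Biopsy is not limited to suspected episodes, because "all subjects will undergo surveillance renal biopsies following reperfusion of the allograft on Day 0 and again at the end of Week 24".

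Protocol 9.5 consists of this: "This is a single-arm, open-label study. No randomization or blinding will be used". Neither document describes masking of the consensus readers, individual grades recorded before discussion, a rule for disagreement, or a bar on a pathologist rating a biopsy that he or she already read for management. Neither cites a reading charter.

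Protocol 6.3 sets the target at 17 or more of 20 subjects free of failure. Protocol 7.1 plans approximately four centers. SAP 2.2.1 still says two.

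**The concern.** The rejection component depends on histologic judgment, and failure begins at grade 1A. Whether a biopsy falls just below or just at 1A is the call most open to influence from knowing how the patient did. As written, a consensus reader may know the local grade, whether steroids were given, how creatinine moved, and whether the biopsy was for cause or surveillance. At the initial two sites the reader may also be the pathologist who gave the local read. For subjects at added sites neither reader gave it, so conditions of reading can differ by site.

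In a randomized trial, leniency common to both arms would largely cancel. Here there is one arm, the count is held against a fixed target, and Protocol 5.6 says that results will be interpreted against outside trials. Any shift at the 1A line passes straight into the reported failure rate.

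**Working it through.** **Inputs.** n = 20 and a limit of 3 failures (Protocol 14.2.6, SAP 2.3); target 17/20 (Protocol 6.3); reference response rate 70% and stated confidence above 89% (Protocol 14.2.6); 80% two-sided exact interval (Protocol 14.2.1.2); historical failure rate 21.7% by 1 year (Protocol 14.2.6, used only as one point in a range). The other true failure rates are assumed.

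**1. The plan's own figure.** Confidence = 1 − P(X ≥ 17 | n = 20, p = 0.70) = 1 − 0.1071 = 89.3%. The stated figure reproduces.

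**2. What one subject is worth at the boundary.**

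| Responders | Confidence that response is at least 70% | 80% exact interval for failure | Target |
|---|---|---|---|
| 17/20 | 89.3% | 5.6% to 30.4% | met |
| 16/20 | 76.2% | 9.0% to 36.1% | missed |

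One changed grade at this point moves confidence by 13.0 points.

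**3. Which direction matters.** The endpoint requires treatment as well as a grade. If consensus lowers a treated local 1A below 1A, a failure can disappear. If consensus raises an untreated biopsy to 1A, that does not by itself make a tBPAR. The favourable error is therefore a downgrade, and a single downgrade changes the target result only when the count is exactly 4 failures. P(X = 4 | n = 20, p) = C(20,4) p⁴(1 − p)¹⁶:

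| True failure rate p | P(exactly 4 failures) |
|---|---|
| 10% | 9.0% |
| 15% | 18.2% |
| 20% | 21.8% |
| 21.7% | 21.4% |

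These are upper bounds on how often one downgrade could decide the result. At least one of the four failures must be a rejection near 1A, in a subject with no other qualifying event.

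**4. Illustration of a systematic shift.** The documents give neither the share of failures that depends on the reader (s) nor the share of those that unmasked reading would drop (d). Assume s = 0.5 or 1 and d = 10% to 30%. The apparent failure rate is p(1 − s·d), and the chance of reaching 17/20 is P(X ≤ 3 | n = 20) at that rate. With true p = 20%:

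- No drop: rate 20%, chance 41%.
- s = 0.5: rate 0.20 × 0.95 = 19% (d = 10%) to 0.20 × 0.85 = 17% (d = 30%), chance 46% to 55%.
- s = 1: rate 0.20 × 0.90 = 18% to 0.20 × 0.70 = 14%, chance 50% to 70%.

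**The case against.** Several points on the other side stand.

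- Protocol 9.5 sits under a heading on randomization and most naturally concerns treatment assignment. A reader might infer that it forbids masked slide reading, or that the endpoint is certain to be read unmasked. The documents do not support either inference. They leave masking of this reading unspecified.
- That the same individual gives both reads is possible, not stated. Protocol 7.1 says only that a local pathologist reads the biopsy.
- The plan does not use the local grade alone. Each rating needs agreement across two sites, and one panel serves all centers. That reduces individual error, but it does not remove shared knowledge of the clinical course or anchoring on the local grade.
- A reader might add the chances of 3 and 4 failures, obtaining 28% to 42% over the same failure rates, and say that one re-graded biopsy decides the result that often. That treats upgrades and downgrades alike, which the treated-rejection definition does not support.
- 17/20 is a target in the primary objective. The analysis is descriptive, with an 80% interval and no formal test. Graft loss and death do not depend on the slide.
- Treated acute rejection is a separate secondary endpoint, as named without a grade threshold, so a treated case downgraded by consensus could still show there. It would not restore the primary count.

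**Conclusion.** The concern holds as an unprotected step in the primary endpoint, not as evidence that readings will be biased. Nothing masks the consensus grade to information that could move a borderline call, and the trial has no control arm to absorb a shift. The probability that the count stands where one downgrade would turn a missed target into a met one is at most 9% to 22% over true failure rates of 10% to 21.7%. At that boundary, confidence in a response rate of at least 70% is 76.2% or 89.3% depending on one subject. The rises from 41% to 46–55% or 50–70% illustrate a sustained shift and rest wholly on the assumed s and d; the upper range takes every failure to be reader-dependent, which is the extreme case.

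A related gap is concrete whatever one thinks of bias: the documents do not say how the treatment requirement combines with the consensus grade when a subject was treated on a local 1A or higher and the consensus is lower. The change should be made. It is inexpensive and leaves patient care as planned.

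**What to change.** In Protocol 14.2.1.1 and SAP 3.5.1.2:

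- The same consensus pathologists grade coded slides in batches, without subject, site, visit, for-cause or surveillance label, local grade, creatinine or treatment given.
- Each reader records a grade before the consensus discussion.
- Any non-histologic input that Banff 2017 needs for antibody-mediated rejection (for example donor-specific antibody results) is supplied only after the histologic grade is recorded.
- State whether a subject treated on a local grade of 1A or higher counts as a tBPAR when the consensus grade is lower.
- Report the primary count by local read as a sensitivity analysis.

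In Protocol 9.5, clarify that the absence of blinding refers to treatment and that the consensus reading is masked as above. Align the SAP's two sites with the protocol's initial two of approximately four. Local reads stay unmasked for patient management.

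The cost is slide coding, batch logistics and a short delay before the consensus grade. No extra reader or biopsy is needed. In a 20-subject trial a reader may still recognise a case, so masking reduces the exposure without removing it. If a reading charter with these rules already exists, citing it in both documents would be enough for the masking part.

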##### **14.2.1.2. Primary Efficacy Analysis**

The primary efficacy endpoint will be analyzed descriptively. The incidence of efficacy failure, defined as tBPAR of grade 1A or higher, graft loss or death, at Week 24 post-transplantation will be calculated, and the corresponding 80% 2-sided exact confidence interval will be calculated.

##### **14.2.1.3. Secondary Efficacy Endpoints**

In addition to Week 24, the incidence of efficacy failure as defined in Section [14.2.1.2](#) will be analyzed at Week 12 and Week 48.

The following secondary efficacy variables will be analyzed at Weeks 12, 24 and 48:

- Incidence of tBPAR, graft loss, death or loss to follow-up (LTFU)
- Incidence of antibody-mediated rejection
- Incidence of tBPAR
- Incidence of BPAR
- Incidence of treated acute rejections
- Proportion of subjects with dnDSA

##### **14.2.1.4. Secondary Efficacy Analyses**

The secondary efficacy endpoints will be analyzed in the same way as the primary efficacy endpoint, at Weeks 12, 24 and 48.

## **14.2.2. Safety**

### **14.2.2.1. Safety Endpoints**

Safety endpoints will include:

- TEAEs and SAEs
- TEAE of special interest
  - Thrombotic and embolic events
  - Hepatic function abnormality (meeting the definition of Hy's Law)
  - Anaphylaxis and clinically significant (CTCAE grade 3 or higher) hypersensitivity reactions
  - Immune complex disease
  - Severe infusion-related reactions (CTCAE Grade 3 or higher)
  - Malignant neoplasm
  - Infections:
    - Clinically significant (CTCAE Grade 3 or higher) infections
    - Opportunistic infections (including but not limited to reactivation of latent viral infection [varicella zoster virus (VZV), herpes simplex virus (HSV), Epstein-Barr virus (EBV), JC virus (JCV), cytomegalovirus (CMV), and BK polyoma virus], fungal infections and tuberculosis
- Laboratory data (laboratory variables by visit, change from baseline of laboratory variables by visit)
- Vital signs (systolic and diastolic blood pressure, pulse rate, respiratory rate, body temperature and body weight) by visit
- ECG by visit

### **14.2.2.2. Safety Analysis**

AEs will be coded using the most recent version of Medical Dictionary for Regulatory Activities (MedDRA). All TEAEs will be summarized overall and by MedDRA System Organ Class and Preferred Term, by severity and by relationship to investigational product. Specific AEs will be counted once for each subject for calculating rates, but will be presented in total in subject listings. In addition, if the same AE occurs multiple times within a particular subject, the highest severity and level of causality will be reported. In addition, SAEs and AEs of special interest (AESIs) will be summarized. Other safety parameters, including laboratory assessments, vital signs, and ECG, will be summarized by absolute value at each visit, together with the corresponding changes from baseline, and shift from baseline if applicable.

#### 14.2.2.3. Immunogenicity

The number and percentage of subjects who develop detectable ADA will be summarized. The impact of ADA on PK and the association with AEs and SAEs will be assessed if data allow.

#### 14.2.3. Analysis of Pharmacokinetics

Descriptive statistics of the VIB4920 plasma concentration will be summarized over visits. Individual and mean plasma concentration-time profiles of VIB4920 will be generated. Non-compartmental analysis will be performed.

When possible, the following PK parameters will be accessed for VIB4920 concentration: maximum observed concentration ( $C_{max}$ ), area under the concentration-time curve (AUC), systemic clearance (CL), and terminal elimination half-life ( $t_{1/2}$ ). Additional PK parameters may be determined and reported as appropriate. Descriptive statistics for PK parameters will be provided.

The potential PK exposure-response relationship for efficacy and safety outcomes with VIB4920 when combined with belatacept will be evaluated in an exploratory manner.

#### 14.2.4. Exploratory endpoints:

- Proportion of subjects with eGFR  $\geq$  60 mL/min at 12, 24 and 48 weeks
- Changes in CCI [REDACTED] between Week 4 and Week 24; Week 4 and Weeks 48; Week 24 and Week 48
- Changes over time in CCI [REDACTED] to VIB4920 pharmacology or disease activity
- Changes over time in the CCI [REDACTED].

#### 14.2.5. Interim Analysis

No interim analysis is planned for the study.

#### 14.2.6. Sample Size and Power Considerations

Belatacept added to standard induction therapy (basiliximab, MMF, corticosteroids) resulted in efficacy failure in 21.7% of recipients of living- and standard criteria deceased-donor kidneys by 1 year (Nulojix® USPI). With 20 subjects, if we observe 3 or fewer subjects with efficacy failure (i.e., response rate  $\geq$  85%) at week 24, we have  $>$  89% confidence that the response rate is at least 70%.

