### **6.3. Primary Objective**

The primary objective is to demonstrate that when added to standard-of-care induction regimen that includes Thymoglobulin® (anti-thymocyte globulin [rabbit]) and corticosteroids, dual costimulation blockade with multiple doses of VIB4920 + belatacept, started at the time of kidney transplant surgery and repeated every 2-4 weeks post-transplantation, prevents composite efficacy failure (tBPAR of grade 1A or higher, graft loss or death) at Week 24 post-transplantation in the majority of subjects ( $\geq 17/20$ ).

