## **7.2. Number of Subjects**

Eligible patients (i.e., meeting all inclusion and exclusion criteria) will be included in the study until a total of 20 patients undergo the scheduled kidney transplant surgery with intention to treat with the revised "full-dose" regimen of Thymoglobulin, extended steroids, and an additional dose of VIB4920 on Day 3 or 4, *and* receive at least one dose of VIB4920.

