2.3 Sample Size

The protocol was amended after 3 subjects were enrolled under the protocol v2.0. Approximately 20 subjects will be enrolled under protocol v3.0.

Belatacept added to standard induction therapy (basiliximab, mycophenolate mofetil, corticosteroids) resulted in efficacy failure in 21.7% of recipients of living- and standard criteria deceased-donor kidneys by 1 year (Nulojix[®] USPI). With 20 subjects, if 3 or fewer subjects are observed with efficacy failure (ie, response rate \geq 85%) at week 24, there is $>$ 89% confidence that the response rate is at least 70%.

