3.3.2 Efficacy evaluable set

Efficacy evaluable set includes all subjects who received the revised regimen of Thymoglobulin and steroids, and any dose of IP. The efficacy analysis will be based on the efficacy evaluable set.

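### Does the Week 24 target of 17 out of 20 need restating for a number of known outcomes other than 20?

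*Protocol*

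**What the plan says.** The target appears in three forms.

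- **Protocol 6.3** (repeated in SAP 2.1, Table 1): composite failure is prevented "at Week 24 post-transplantation in the majority of subjects", given as at least 17/20.
- **Protocol 14.2.6**: "With 20 subjects, if we observe 3 or fewer subjects with efficacy failure", glossed as a response rate of at least 85%, the confidence claim is more than "89% confidence that the response rate is at least 70" per cent.
- **SAP 2.3**: the same statement, opening "With 20 subjects, if 3 or fewer subjects are observed with efficacy failure".

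On numbers, Protocol 7.2 enrols "until a total of 20 patients undergo the scheduled kidney transplant surgery with intention to treat with the revised" regimen and have had at least one VIB4920 dose. Protocol 7.1 says about 20, and SAP 2.3 says "Approximately 20 subjects will be enrolled under protocol v3.0". Protocol 8.3 does not replace subjects who leave after a dose.

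On the denominator, Protocol 14.1.1.2 states: "Efficacy evaluable set includes all subjects who received the revised regimen of Thymoglobulin and steroids, and any dose of IP". SAP 3.3.2 has the same definition and adds: "The efficacy analysis will be based on the efficacy evaluable set". Protocol 14.1.2 limits analyses to observed data, and both it and SAP 3.5.1.2 rule out imputation.

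On the analysis, Protocol 14.2.1.2 and SAP 3.5.1.2 call it descriptive: the incidence of failure with an 80% two-sided exact confidence interval. SAP 4.1 runs it once every subject has reached Week 24 or withdrawn. Protocol 14.2.1.3 and SAP 3.5.2.1 add a composite, also at Week 24, in which loss to follow-up counts as an event.

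**The concern.** The primary objective is worded as a demonstration against a count, and that count is tied to 20 subjects. The plan itself makes another number possible. Enrolment is approximate in two places, dosed subjects are not replaced, withdrawal before Week 24 is foreseen, and enrolment counts intention to give the revised regimen while the efficacy set counts its receipt.

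For an event-free withdrawal, two statements seem to pull apart. The efficacy set asks for no Week 24 outcome, so the subject stays in. The observed-data rule could be read as taking the subject out. If the choice changed whether the objective was met, and were made in an open-label study with outcomes known, the headline result could depend on a decision taken after the fact. The 89% figure would also be quoted for a number of subjects at which it does not hold.

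**Working it through.** **1. The plan's own figure.** Inputs: n = 20, up to 3 failures, reference response 70% (Protocol 14.2.6). Confidence that response is at least 70% is 1 − P(X ≤ 3), with X ~ Binomial(20, 0.30):

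1 − (0.0008 + 0.0068 + 0.0278 + 0.0716) = 1 − 0.1071 = 0.8929.

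This reproduces the stated figure of more than 89%. The claim is conditional on 20 subjects, so it is correct as written and is not made for any other number.

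**2. The boundary case: 20 treated, 3 failures, 1 event-free withdrawal.**

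| Handling of the withdrawal | Response | Confidence in ≥70% | 3 or fewer failures | ≥85% | ≥17 responders |
|---|---|---|---|---|---|
| Kept as non-failure | 17/20 = 85.0% | 89.3% | met | met | met |
| Removed | 16/19 = 84.2% | 86.7% | met | not met | not met |

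The 86.7% is 1 − P(X ≤ 3) with X ~ Binomial(19, 0.30). The failure-count column does not change. A reversal needs two moves together: removing the subject, and leaving the failure count for another form of the target.

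**3. How often the readings differ.** The documents give no dropout rate, so this rests on assumptions: true response 85%, and each subject's status unknown with probability u, independently of outcome. The comparison is between all 20 kept with 3 or fewer failures and the unknowns removed under each form.

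| Form applied after removal | Disagreement with kept reading |
|---|---|
| 3 or fewer failures | 0% at any u |
| ≥85% of those observed | 8.1% (u = 2%), 15.5% (u = 5%), 21.0% (u = 10%) |
| ≥17 observed responders | 23.9% (u = 5%) |

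For the 85% form with 1 to 6 unknowns, disagreement arises only at exactly 3 failures. For the 17-responder form it is wider: 2 failures with 2 removed leaves 16 responders of 18, short of 17, while the kept reading is 18/20. All the disagreement comes from changing the form. An unknown rate of 5% also implies a 1 − 0.95^20 = 64% chance of at least one unknown among 20, against follow-up that continues after drug is stopped (Protocol 7.1 and 8.3).

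**4. Which denominator the documents support.** The efficacy analysis is assigned to a set defined by treatment received, with no outcome requirement. The endpoint is the incidence of an event, so a subject with no recorded event is not plainly a missing value. A separate composite that adds loss to follow-up makes most sense if such subjects otherwise count as non-failures in the denominator. A ban on imputation does not say to exclude. Keeping the subject is therefore the natural reading, though not a stated one.

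**5. What writing a rule would do.** Making ≥85% the governing form keeps confidence above 89% for every n from 16 to 24, but at 16 to 19 it allows 2 failures rather than 3. If unknowns were also removed, the chance of meeting the target at 85% response and u = 5% would be 52.9%, against 68.4% under the kept reading. That tightens the criterion. A side table with all unknowns counted as failures would add only consent withdrawals to the planned loss-to-follow-up composite.

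**The case for a change.** The strongest case for a change is that the objective says the trial is to demonstrate something against a number, so calling the analysis descriptive does not remove the criterion, and a reported proportion needs a denominator in any event. The loss-to-follow-up composite is secondary, and Protocol 8.3 describes loss to follow-up as non-attendance with no stated wish to withdraw, so withdrawal of consent is not clearly caught. Follow-up after stopping drug reduces unknowns without removing them. The study is open-label, and one sentence would settle the matter at no cost in patients or data.

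Part of this stands. The denominator is not put in words, the observed-data rule leaves some doubt, and consent withdrawal does sit outside the described meaning of loss to follow-up. What does not stand is the claim that the same data give opposite answers. That holds only if the form of the target is switched along with the denominator, and the section setting out the confidence claim counts failures. Choice after the fact is a possibility, not something the documents point to: the sponsor's periodic review in Protocol 7.5 concerns safety data, and Protocol 14.2.5 plans no interim analysis.

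**Conclusion.** No change to the plan is needed. The target and its confidence figure are correct for the 20 subjects they are stated for. What is missing is a detail that an analyst can fill from the text: the denominator is the efficacy evaluable set, an event-free withdrawal stays in it as a non-failure, and the report gives the exact confidence for the number analysed.

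At 3 failures and 1 withdrawal, the choice moves the estimate from 85.0% to 84.2% and the confidence from 89.3% to 86.7%, with the failure-count target met both ways. Any reader can redo that sum, in a 20-subject exploratory study that Protocol 5.6 says will be interpreted against outside trial results and current practice.

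The conclusion rests on the descriptive status of the analysis and on reading the efficacy set as the denominator. It would be weaker if a formal pass or fail decision were attached to the percentage form with unknowns removed. The disagreement rates of 8.1% to 21.0% for that form depend on assumed dropout of 2% to 10%.

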#### **5.1.3.2. Blocking the CD40-CD40L pathway**

The experience with blocking the CD40-CD40L ligand pathway in human transplantation is limited. Preliminary results with BG9588 (hu5C8, a humanized anti-CD40L monoclonal antibody [mAb]) in combination with MMF in kidney transplantation showed mild, steroid-sensitive acute rejection early in the post-transplant period in 5/7 patients, including two who received hu5C8 as monotherapy. These mild rejection episodes have been easily reversed with steroids and long-term good renal function was achieved in all patients (Kirk, Knechtle et al. 2001). The study drug was well tolerated during the infusion but thromboembolic events in this study and other studies with hu5C8 in non-transplant indications led to discontinuation of hu5C8 development.

Recently, CFZ533 a fully human, Fc-silenced, nondepleting, IgG1 mAb against CD40 was compared to tacrolimus following basiliximab induction in patients receiving kidney transplants. Six-month interim results demonstrated comparable efficacy on the composite endpoint of treated biopsy-proven acute rejection, graft loss, or death (21.2 vs. 22.2%) and better renal function (55.8 vs. 45.5 mL/min) with CFZ533 vs. tacrolimus, respectively, with fewer infectious complications in the CFZ533 group (Nashan, Tedesco et al. 2018).

These studies demonstrate that combining belatacept with an mTOR inhibitor effectively prevents kidney allograft rejection without CNIs or steroids when used following T cell depleting induction with alemtuzumab or Thymoglobulin and that selected, immunologically low-risk patients can be maintained safely on once monthly intravenous (IV) belatacept. Experience with blocking the CD40-CD40L pathway in human kidney transplant is limited but early results show promising efficacy. These data together with the existing preclinical evidence supporting the synergistic effect of simultaneously blocking the CD28-CD80/86 and CD40-CD40L pathways provide the scientific and clinical foundation for the rationale of combining belatacept and VIB4920 to prevent allograft rejection and preserve renal function without the use of conventional immunosuppression.

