## **5.6. Rationale for Study Population**

The study population is low immunological risk adult recipients of a first kidney allograft from a standard criteria deceased donor, living unrelated or human leukocyte antigen (HLA) non-identical living related donor, typical for early development studies of new immunosuppression regimens in kidney transplantation.

This is a single-arm, open-label exploratory study without a concurrent control group. The results of this study will be interpreted in the context of efficacy results from patients in randomized, controlled trials treated with a Food and Drug Administration (FDA)-approved standard-of-care composed of tacrolimus (TAC), MMF and corticosteroids and outcomes of standard of care therapies in current clinical practice. Results of this study will be used to inform the dose and regimen selection for investigation in later phases of clinical development.

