2 STUDY OVERVIEW

2.1 Study Objectives and Endpoints

The objectives and corresponding endpoints are listed in [Table 1](#) below:

Table 1 Study Objectives and Endpoints

| Primary objective | Endpoints/variables |
|---|--|
| 
 To demonstrate that, when added to standard-of-care induction regimen that includes Thymoglobulin® (anti-thymocyte globulin [rabbit]) and corticosteroids, dual costimulation blockade with multiple doses of VIB4920 + belatacept, started at the time of kidney transplant surgery and repeated every 2-4 weeks post-transplantation, prevents composite efficacy failure (tBPAR of grade 1A or higher, graft loss, or death) at Week 24 post-transplantation in the majority of subjects ($\geq 17/20$) | 
 Incidence of efficacy failure, defined as treated biopsy-proven acute rejection (tBPAR) of grade 1A or higher, graft loss, or death, at Week 24 post-transplantation |
| Secondary objectives | Endpoints/variables |
| 
 To evaluate individual components (and combinations of the individual components) of the composite efficacy endpoint at Weeks 12, 24, and 48 post-transplantation. | 
 Incidence of efficacy failure, defined as treated biopsy-proven acute rejection (tBPAR) of grade 1A or higher, graft loss, or death, at Weeks 12 and 48 post-transplantation Incidence of tBPAR, graft loss, death, or loss to follow-up at Weeks 12, 24, and 48 post-transplantation Incidence of antibody-mediated rejection at Weeks 12, 24, and 48 post-transplantation Incidence of tBPAR at Weeks 12, 24, and 48 post-transplantation Incidence of BPAR at Weeks 12, 24, and 48 post-transplantation Incidence of treated acute rejections at Weeks 12, 24, and 48 post-transplantation Proportion of subjects with de novo donor-specific antibodies (dnDSA) at Weeks 12, 24, and 48 post-transplantation |
| 
 To evaluate safety and tolerability of dual costimulation blockade with VIB4920 + | 
 Treatment-emergent adverse events and treatment-emergent serious adverse events (TEAE and TESAE) |

Table 1 Study Objectives and Endpoints

| | |
|---|---|
| belatacept in subjects receiving a kidney transplant | 
 • Treatment-emergent adverse events of special interest (TEAESI) • Laboratory data by visit • Vital signs data by visit • ECG data by visit |

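### Is a 70% response floor too low for the 17/20 rule when the cited belatacept failure rate implies 78.3% response?

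*Protocol*

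**What the plan says.** Protocol section 14.2.6 opens with an external rate: belatacept added to basiliximab, MMF and corticosteroids "resulted in efficacy failure in 21.7% of recipients of living- and standard criteria deceased-donor kidneys by 1 year". It then says that 3 or fewer failures among 20 subjects at Week 24 would give more than "89% confidence that the response rate is at least 70" per cent. SAP section 2.3 repeats both statements with the same numbers. Neither section gives a null rate, a type I error or a power, and neither gives a reason for 70%.

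The 17/20 mark sits in the primary objective, where it spells out what a majority of subjects means. Protocol section 6.3 begins "The primary objective is to demonstrate that when added to standard-of-care induction regimen", and Table 1 in SAP section 2.1 has "To demonstrate that, when added to standard-of-care induction regimen that includes".

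The analysis is estimation only. Protocol section 14.2.1.2 says "The primary efficacy endpoint will be analyzed descriptively", and SAP section 3.5.1.2 adds that "the corresponding 80% 2-sided exact confidence interval will be calculated". There is no hypothesis test.

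Two other places bear on interpretation. Protocol section 5.1.3.2 reports six-month interim results for an anti-CD40 antibody against tacrolimus, with "comparable efficacy on the composite endpoint of treated biopsy-proven acute rejection, graft loss, or death (21.2 vs. 22.2" per cent. Protocol section 5.6 says "The results of this study will be interpreted in the context of efficacy results from patients in randomized, controlled trials" of tacrolimus, MMF and corticosteroids, and in the context of current practice.

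**The concern.** A reader who meets 21.7% failure and then, one sentence later, a 70% response floor expects the two to be connected. They are not: 70% is 8.3 points below the implied 78.3%. It is also below the response rates implied by section 5.1.3.2, which are 78.8% and 77.8%. The objective is phrased as a demonstration with a numerical pass mark, and section 5.6 promises a reading against outside trials. If a pass at 17/20 were presented as an advance on existing regimens, it would claim more than 20 subjects can show, and neither document states how often an ordinary regimen would pass. At stake is the reading of the primary result when it falls at or just above the mark.

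**Working it through.** **Inputs.** n = 20 and a mark of 3 or fewer failures (Protocol 14.2.6, SAP 2.3); floor of 70% response, or 30% failure (same sections); cited failure rate 21.7%, so response 100 − 21.7 = 78.3%; six-month failure rates 21.2% and 22.2% (Protocol 5.1.3.2); planned interval 80% two-sided exact (Protocol 14.2.1.2, SAP 3.5.1.2).

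**Step 1: the plan's own figure.** With X failures and true failure rate p,

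P(X ≤ 3) = Σ C(20, k) p^k (1 − p)^(20−k), k = 0 to 3.

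At p = 0.30 the four terms are 0.00080 + 0.00684 + 0.02785 + 0.07160 = 0.1071. The confidence is 1 − 0.1071 = 0.8929, or 89.3%. The stated value of more than 89% reproduces.

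**Step 2: agreement with the planned interval.** For r responders, the exact 80% limits are the 10th percentile of Beta(r, 21 − r) and the 90th percentile of Beta(r + 1, 20 − r). At r = 17 these are 69.6% and 94.4%. Each side of an 80% interval carries 90% confidence. Since 89.3% falls just short of 90%, a lower limit just under 70% is what the sample-size statement implies. The two are consistent.

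**Step 3: does 17/20 support the stated objective?** At p = 0.50, P(X ≤ 3) = 0.0013. A true response of only one half would give 17 or more responders 0.13% of the time. A majority response is well supported at the mark.

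**Step 4: what each result says about 78.3%.** The confidence that failure is below 21.7% is 1 − P(X ≤ x | p = 0.217).

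| Result | 80% exact interval for response | Confidence that failure is below 21.7% |
|---|---|---|
| 17/20 | 69.6% to 94.4% | 1 − 0.3407 = 65.9% |
| 18/20 | 75.5% to 97.3% | 1 − 0.1586 = 84.1% |
| 19/20 | 81.9% to 99.5% | 1 − 0.0491 = 95.1% |

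The first result whose planned interval excludes 78.3% is 19/20. At 17/20 and 18/20 the interval contains it, and the reader will see that.

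**Step 5: how often the mark is met.** P(X ≤ 3) is 10.7% at 30% true failure, 32.1% at 22.2%, 34.1% at 21.7%, 36.1% at 21.2% and 86.7% at 10%.

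**Step 6: is the 8.3-point gap meaningful?** The 70% is a lower confidence limit, whereas 78.3% is a point estimate. Like with like, the mark is 17/20 = 85%, which is 85 − 78.3 = 6.7 points above the cited rate. With 20 subjects, a lower limit below a nearby reference rate is expected.

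**The case for a change.** The strongest case for a change is that the section offers one benchmark and then argues from another number without explanation. A regimen no better than the benchmark passes about one time in three, and the results are meant to be read against outside trials and to inform later development. The time mismatch does not help the plan. Failures accumulate, so the Week 24 response on the cited regimen would be at least 78.3%. If it were 80%, 82% or 85% (assumed values), the confidence of exceeding it at 17/20 would be 58.9%, 49.7% or 35.2%. Three remedies are possible: add the operating characteristics, report the exact confidence against 21.7%, and soften the verb in the objective.

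Part of this stands. The 70% is unexplained and the operating characteristics are absent. It does not follow that the plan must change.

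- No section claims improvement on 21.7%. The primary hypothesis (Protocol 6.1) is prevention of rejection without traditional maintenance immunosuppression, and the study rationale (Protocol 5.3) is about replacing standard therapy. Neither requires fewer failures than existing regimens.
- The outside rates are not like for like. The 21.7% is a 1-year rate after basiliximab with MMF and steroids, whereas this trial uses Thymoglobulin, stops steroids after Day 28 and measures at Week 24. The section 5.1.3.2 rates are interim results after basiliximab.
- Results of 17 or 18 together have probability 0.8670 − 0.3917 = 47.5% at 90% true response and 0.6477 − 0.1756 = 47.2% at 85%. A bare pass is strictly 17/20, with probability 0.8670 − 0.6769 = 19.0% and 0.6477 − 0.4049 = 24.3%.
- A confidence statement against 21.7% in the primary analysis would invite the cross-trial reading it is meant to guard against. Whether to add it is a matter of judgement.
- Replacing *demonstrate* with *estimate* does not fit an objective that keeps the 17/20 mark, and it alters no analysis.

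**Conclusion.** No change follows. The only figure the plan states is right (89.3% against a stated value above 89%), it agrees with the planned 80% interval, and the mark supports the objective actually written, a majority response. Followed as it stands, the plan gives a sound estimate, with an interval that shows how far the result is from settling any comparison with 78.3%. The missing reason for 70% is a small gap in justification. An analyst writing the report can supply the context, including the 34.1% chance of passing at the cited rate, without touching the sample size, the mark, the analysis or the objective.

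This rests on 20 evaluable subjects with known Week 24 status and independent outcomes, and on the outside rates as the protocol prints them. It would need revisiting only if the report used a pass at 17/20 or 18/20 to claim superiority over an existing regimen, which neither document proposes.
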